3.4 Analysis of secondary outcome measures

Symptoms of acute hyponatraemia (nausea, vomiting, headache, seizures) within the first 72 hours post-transplant

The number and percentage of participants experiencing each symptom will be presented by trial arm and overall. The proportion of participants experiencing each symptom at least once will be compared with exact logistic regression, because the number experiencing these symptoms may be small. The model will be adjusted for donor type (living vs deceased donor) and participant weight (<20kg vs ≥20kg pretransplant).

Statistical Analysis Plan

The degree of fluid overload experienced

This outcome is defined as proportional increase in patient weight between pretransplant weight and maximum weight in the 72 hours post-transplant. The mean proportional weight increase, with standard deviation, will be presented for each trial arm and overall. A Normal linear regression model will be used to assess whether mean proportional weight increase is different between the two treatment arms, adjusting for donor type (living vs deceased donor), participant weight pre transplant (<20kg vs ≥20kg pre-transplant) and transplant centre as a random effect. Residual plots from the normal linear regression will be examined. If there is any evidence of skew or non-constant variance, normal linear regression of log-transformed proportional weight increase will be used to assess whether mean log- proportional weight increase are different between the two treatment arms, adjusting for donor type (living vs deceased donor), participant weight pre transplant (<20kg vs ≥20kg pre-transplant) and transplant centre as a random effect.

Time to discharge from hospital

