- Magnitude of variation in plasma sodium concentration in first 72h For each participant, the difference between their maximum and minimum plasma sodium concentration between transplant operation start and 72 hours post transplant, will be calculated. This outcome is clinically important as variation leads to fluid shifts, brain oedema and seizures. The mean magnitude of variation, with standard deviation, will be presented for each trial arm and overall. A Normal linear regression model will be used to assess whether mean magnitude of variation is different between the two treatment arms, adjusting for donor type (living vs deceased donor), participant weight pre transplant (<20kg vs ≥20kg pre-transplant) and transplant centre as a random effect. Residual plots from the normal linear regression will be examined. If there is any evidence of skew or non-constant variance, normal linear regression of log-transformed magnitude of variation will be used to assess whether mean log- magnitude of variation are different between the two treatment arms, adjusting for donor type (living vs deceased donor), participant weight pre transplant (<20kg vs ≥20kg pre-transplant) and transplant centre as a random effect.
- Maximum rate of change of plasma sodium concentration in first 72h

(Template Version 07/10/08)

effect.

Statistical Analysis Plan

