For each participant, all plasma sodium concentrations measurements which are ≥5mmol/l and which were taken between transplant operation start and 72 hours post-transplant will be compared. The rate of change will be calculated, for tests taken at least six hours apart, by taking the difference between the measurements and dividing by the number of hours between the measurements. The maximum decrease of these will be selected for each participant. The mean maximum rate, with standard deviation, will be presented for each trial arm and overall. A Normal linear regression model will be used to assess whether mean maximum rate is different between the two treatment arms, adjusting for donor type (living vs deceased donor), participant weight pre transplant (<20kg vs ≥20kg pre-transplant) and transplant centre as a random effect. Residual plots from the normal linear regression will be examined. If there is any evidence of skew or non-constant variance, normal linear regression of log-transformed maximum rate will be used to assess whether mean log- maximum rate are different between the two treatment arms, adjusting for donor type (living vs deceased donor), participant weight pre transplant (<20kg vs ≥20kg pretransplant) and transplant centre as a random effect.

Serious adverse events

Serious adverse events will be tabulated by classification (Acute severe hyponatraemia – symptomatic and non-symptomatic (separately), severe hyperkalaemia, seizures and other) and treatment arm. The number of participants who experienced at least one SAE will also be presented. Following the implementation of protocol v2.0, SAEs relating to electrolytes were no longer required to be reported by sites. Therefore, both acute severe hyponatraemia and severe hyperkalaemia will also be identified through all participants' plasma and blood gas results, including those SAEs which occurred prior to the protocol change. Acute severe hyponatraemia is defined as: a fall in plasma or blood gas sodium concentration of ≥10mmol/L from the pre transplant level or a rate of fall of plasma or blood gas sodium concentration exceeding 1mmol/L/hour averaged over 6 hours. A plasma or blood gas potassium concentration >6.5mmol/L will be used to identify acute severe hyperkalaemia. No statistical testing will be conducted.

Graft and patient survival at 90 days

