3.8 Procedures for handling Missing Data

Any missing primary and secondary outcome data will be summarised. For the primary outcome and other blood test results, the result will be considered missing if there are no results for that measurement within the 72-hour period post transplant. It is anticipated that missing data for the primary outcome will be rare, as the plasma sodium measurement is also used to determine one of the key SAEs within the trial, which mandates immediate reporting. Missing data due to death or withdrawal are also anticipated to be very rare: data from the UKTR showed that the 1-year patient survival rate for those transplanted between 2015-2018 was 99% (95% confidence interval 96-100) for paediatric kidney transplants from living and DBD donors (5). Primary and secondary outcome measures will not be imputed and these will be treated as missing data and excluded from the relevant analyses. If outcome data is missing for more than 25% of participants, outcomes will not be reported.

To explore if missing values have an undue impact on the primary outcome result, a sensitivity analysis using multiple imputation will be performed if the primary outcome is missing in more than 5% of the participants included in the modified intention to treat analysis. Variables will be included in the imputation model if they have a completeness of ≥65% and these variables are:

- Donor: type, age, ethnicity, BMI
- Trial participant/Recipient: age, sex, ethnicity, cause of end stage kidney disease, native urine output, dialysis type, weight and height at transplant, systolic blood pressure, blood group, calculated reaction frequency, graft number
- Transplant: blood group match, transplanting centre, cold ischaemic time, HLA mismatch between donor and recipient, graft placement.

Forty imputations will be used and the average across the imputations will be calculated. The model specified in section 3.3 will be utilised.

If the proportion of participants with a missing primary outcome is less than or equal to 5% then this sensitivity analysis will not be performed.

Statistical Analysis Plan

All the risk adjustment factors will always be known, as weight and site are required for randomisation and donor type is mandatory data required by the UKTR.

4. Data Analysis Tables

Data analysis will be based on the following tables.

- 4.1 Screening, Recruitment and Follow-up tables
 - 4.1.1 Recruitment by Centre

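### The log fallback for fluid overload is undefined for a child who gains no weight, so such children would leave the comparison because of their outcome

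*SAP*

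**What the plan says.** SAP section 3.4 defines fluid overload as the "proportional increase in patient weight between pretransplant weight and maximum weight in the 72 hours post-transplant". It gives no formula. The planned model is a normal linear regression with donor type, weight group and a random centre effect. The switch is set as follows: on any sign of skew or unequal variance in the residual plots, "normal linear regression of log-transformed proportional weight increase will be used". No offset, alternative method or rule for values at or below zero is given.

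Section 3.5 uses the same switch for two sodium outcomes. For the maximum rate of change, each rate is obtained "by taking the difference between the measurements and dividing by the number of hours between the measurements", then "The maximum decrease of these will be selected for each participant", and under skew "normal linear regression of log-transformed maximum rate will be used". For the maximum-minus-minimum difference, "normal linear regression of log-transformed magnitude of variation will be used".

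On missing values, section 3.8 states: "Primary and secondary outcome measures will not be imputed and these will be treated as missing data and excluded from the relevant analyses". Section 3.2 names SAS as the software.

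**The concern.** A relative weight change can be zero or negative, and its logarithm then does not exist. SAS returns a missing value, and the regression omits the child. The weight itself was observed; only its transformed value is lost. Nothing in the plan brings the child back, since section 3.8 rules out imputation.

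The children lost are those with no overload by the trial's own measure. If the fluids differ in their effect on weight, the arms lose different numbers, and the comparison is no longer between the groups as randomised. The alternative is an offset or other repair chosen once the data are open, which a prespecified plan should avoid. Section 3.2 sets out a stepwise plan for separation in the logistic models; there is no counterpart here.

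**Working it through.** **1. Domain check** (illustrative weights), with x = (maximum weight − pre-transplant weight) / pre-transplant weight:

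| Pre, max (kg) | x | log(x) | log(max/pre) |
|---|---|---|---|
| 20, 21 | 0.05 | −3.00 | 0.049 |
| 20, 20 | 0 | undefined | 0 |
| 20, 19.6 | −0.02 | undefined | −0.020 |

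**2. Share of children affected.** The SAP has no figure to reproduce, so means and SDs are assumptions. For a normal x, P(x ≤ 0) = Φ(−mean/SD). The last column applies this to the 128 patients in section 1.6.

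| Mean, SD | Φ(−mean/SD) | Share | Of 128 |
|---|---|---|---|
| 10%, 3% | Φ(−3.33) | 0.04% | 0 |
| 10%, 5% | Φ(−2.00) | 2.3% | 3 |
| 5%, 3% | Φ(−1.67) | 4.8% | 6 |
| 5%, 4% | Φ(−1.25) | 10.6% | 14 |
| 5%, 5% | Φ(−1.00) | 15.9% | 20 |
| 3%, 4% | Φ(−0.75) | 22.7% | 29 |
| 3%, 5% | Φ(−0.60) | 27.4% | 35 |

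**3. Selection by arm.** Assume means of 6% and 3% with SD 4%. The arms lose Φ(−1.5) = 6.7% and Φ(−0.75) = 22.7%. The mean among those kept is mean + SD × φ(mean/SD)/Φ(mean/SD):
- 6 + 4 × 0.1295/0.9332 = 6.56%
- 3 + 4 × 0.3011/0.7734 = 4.56%

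The difference among those kept is 2.0 points instead of 3.0. With means 8% and 5% and SD 5%, the losses are 5.5% and 15.9%, and the difference is 2.15 instead of 3.0.

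**4. Power** (simulation, 64 per arm, two-sample t-test). These compare the log of x after dropping x ≤ 0 with log(max/pre) on all children:
- Normal, 6% v 3%, SD 4%: about 77–79% v 99%.
- Gamma, mean 6%, SD 4%, shifted by 2 points, about 12% of one arm dropped: about 74% v 82–83%.
- A right-skewed shifted lognormal, 0.1% v 15% dropped: 95% v 96%.

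The loss ranges from large to negligible with the assumed shape.

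**5. Would log(max/pre) cure the skew?** It equals log(1 + x). For a gamma x with mean 5% and SD 4%, its correlation with x is 0.9995, and skewness falls only from 1.60 to 1.43. It keeps every child but leaves the skew.

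**6. Sodium outcomes.** The share with no fall between tests at least six hours apart was simulated. Assumptions: independent noise with SD 2 mmol/L, values rounded to integers, mean sodium flat or rising by up to 6 mmol/L. Results: 9–48% with 4 tests in 72 hours, 0.7–11% with 6, 0.06–1.8% with 8, and about none with 13. If the rate is taken as later minus earlier, every fall is negative and none can be logged. Maximum minus minimum is never negative; it is zero only with a single test or identical values.

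**The case against.** Several counter-arguments carry weight.

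- The loss arises only if the switch is made. In the normal scenario of step 3, a formal skewness test on residuals was positive in only about 5% of simulated trials, so the plan would usually stay on the raw scale, drop nobody and keep about 99% power. This stands against using that scenario as a forecast. However, the trigger is any evidence of skew, judged from plots, which is a low bar, and the defect applies whenever it is met.
- If the outcome was meant as the ratio of maximum to pre-transplant weight, its log always exists. The SAP gives no formula, and the word increase points to relative change. Stating the formula would settle this.
- Section 1.6 says that fluid delivery after transplant well exceeds maintenance needs. Most children may therefore gain weight, and the true share may lie at the low end.
- Sampling appears frequent, since section 1.4 collects all results up to Day 3. A child with no sodium fall should then be rare. For that outcome the gap lies first in the definition: such a child has no assigned value even before any log.
- Unadjusted means and SDs are still to be tabulated, and section 3.2 says that the trial is powered only for the primary outcome.

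A reader might infer that the fallback necessarily loses power, that it always shrinks the difference, or that the three outcomes are equally exposed. The documents support none of these. There are no weight data to fix the distribution, the power loss varies with shape, and the sodium outcomes are only slightly exposed under frequent sampling. Nor does the SAP say in words that these children are excluded; that follows from the undefined log.

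**Conclusion.** The point holds for fluid overload, a secondary outcome. As written, the fallback cannot be applied to a child without weight gain, and following it removes children because of their outcome, possibly unequally by arm. This rests on the relative-change reading and on the switch being triggered. The affected share, under 1% to 27%, rests wholly on the assumed means, SDs and normal shape. No general statement about power can be made. The two sodium outcomes share the wording problem in a minor form. The primary outcome is untouched.

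**What to change.** In section 3.4:
- Write out the formula for the proportional weight increase.
- Replace the log fallback by the same model on the untransformed scale, with robust (sandwich) or bootstrap standard errors. Name which will be used. Section 4.1.1 lists nine centres, so a sandwich estimator clustered on centre would rest on few clusters; resampling participants within centre and arm avoids this.
- Say that the p-value in this case comes from the robust or bootstrap inference, as an exception to the likelihood ratio test in section 3.2.
- State that no child is dropped for a zero or negative value.

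In section 3.5, apply the same rule to the maximum rate of sodium fall and to sodium variation. For the rate, also fix the direction of subtraction and the value given to a child with no fall.

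The log of maximum over pre-transplant weight is also defined for every child, but it would do little about skew.

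The cost is SAP wording only, with no new data. The downside is that the result stays an absolute mean difference, and skew is handled through the standard errors rather than removed.

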2.1 CRF descriptions and data collection schedule

| Form No. | Form Title / Description of Form | Tick if Optional |
|----------|----------------------------------|------------------|
| 1 | Screening Form | |
| 2 | Eligibility assessment | |
| 3 | Baseline Characteristics | |
| 4 | Randomisation | |
| 5 | Transplant Operation | |
| 6 | Day 1 | |

Statistical Analysis Plan

| 7 | Day 2 | |
|------|-------------------------------------|-------------|
| 8 | Day 3 | |
| 9 | Fluids | |
| 10 | Medication & Blood Products | |
| 11 | Day 7 | |
| 12 | End Of Study | |
| 13 A | SAE | \boxtimes |
| 13 B | SAE Narrative | \boxtimes |
| 14 | Additional Medications (for SUSARs) | |
| 15 | SAE CTU Use | \boxtimes |
| 16 | Withdrawal | \boxtimes |

The Trial Visit Schedule shows details of assessments to be performed as follows:

| VISITS | | | | | | | | | |
|----------------------------------|-----------|----------------------|----------|-------------------------|-------------------------|-------------------------|-------------------------|---------------------------|-----------------------|
| | Screening | Baseline (Pre-Tx) | At Tx | Day 1 Post- Tx | Day 2 Post- Tx | Day 3 Post- Tx | Day 7 Post- Tx | Month 3 Post- Tx | Hospital Discharge |
| ENROLMENT | | | | | | | | | |
| Eligibility assessment | x | | | | | | | | |
| Informed consent | | Х | | | | | | | |
| Baseline Characteristics* | | | X | | | | | | |
| Re-confirm consent | | | X | | | | | | |
| Randomisation | | | X | | | | | | |
| TREATMENT | | | | | | | | | |
| Administration of trial fluid** | | | Х | Х | Х | Х | | | |
| ASSESSMENTS | i | | | | | | | | |
| Transplant Operation Data | | | Х | | | | | | |
| Blood Results*** | | Х | X | Х | Х | Х | | | |
| Blood Gas Results (venous) | | x | x | x | x | x | | | |
| Patient Weight | | Х | Х | Х | Х | Х | | | |

Statistical Analysis Plan

| Fluid Data | X | Х | Х | Х | | | |
|-----------------|---|---|---|---|---|---|---|
| Medication | | Х | Х | Х | | | |
| Data | | ^ | ^ | ^ | | | |
| Symptom | | Х | X | X | | | |
| Assessment | | ^ | ^ | ^ | | | |
| Safety | | | | | | | |
| Reporting (see | X | X | X | X | | | |
| section 13) | | | | | | | |
| Transplant | | | | | X | X | |
| Graft Function* | | | | | ^ | ^ | |
| Discharge Date | | | | | | | Х |

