This outcome will be measured from transplant operation start time ("knife to skin") till discharge from hospital, measured in days and will be estimated using competing risks analysis. Discharge from hospital will be considered as the event and death prior to discharge will be considered as the competing risk. Median (IQR) hospital stay from the cumulative incidence curve will be reported for each trial arm and overall. Although if there are no deaths, the Kaplan-Meier method will be used. To accommodate a random centre effect and adjustment for participant weight and donor type, Cox regression analysis with a frailty term will be used to compare time to discharge between treatment arms. Participants who have not been discharged will be censored at the point of last contact. Participants who die will be censored. The estimate of the hazard of discharge from this model should be interpreted with caution because it does not properly account for the competing risk of death. However, since the number of deaths is predicted to be small, the impact of the competing risk is likely to be negligible. This will be explored by examining the cumulative incidence function for death.

Transplant kidney function at 1, 3, 7 and 90 days

This will be calculated using the creatinine-based univariate Schwartz formula (4) to determine eGFR:

eGFR = 36.5 x (height/ plasma creatinine concentration)

where height is measured in cm and plasma creatinine in micromol/L (1mg/dl = 0.01131222 micromol/L). For day 1 and 3, this data will be obtained from the blood data measurements taken routinely. If multiple measurements are recorded on the same day, then we will use the last measurement taken for each day, as this is likely to be the lowest and gives most time for creatinine to be in steady state. For day 7 and 90 a single measurement is being collected via the MACRO database and UK Transplant Registry respectively. For day 1, 3 and 7, the participant height recorded at transplant will be used. For 90 days, the participant's height at this timepoint will be used, which will be obtained from the UKTR. The mean and standard deviation of eGFR at each timepoint will be presented by trial arm and overall.

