A repeated measures mixed Normal linear regression will be used to assess whether kidney function over days 1,3 and 7 are different between the two treatment arms, adjusting for donor type (living vs deceased donor), participant weight pre transplant (<20kg vs ≥20kg pre-transplant) and day of measurement. In addition, two random

Statistical Analysis Plan

effects will be included in the model to account for individual participant effects and transplant centre. Residual plots from the normal linear regression will be examined. If there is any evidence of skew or non-constant variance, repeated measures mixed normal linear regression of log-transformed eGFR will be used to assess whether mean log- eGFR are different between the two treatment arms, adjusting for donor type (living vs deceased donor), participant weight pre transplant (<20kg vs ≥20kg pre-transplant) and participant and transplant centre as random effects.

A separate mixed Normal linear regression will be used to assess whether mean eGFR is different between the two treatment arms at day 90, adjusting for donor type (living vs deceased donor), participant weight pre transplant (<20kg vs ≥20kg pre-transplant) and transplant centre as a random effect. Residual plots from the normal linear regression will be examined. If there is any evidence of skew or non-constant variance, mixed normal linear regression of log-transformed eGFR at 90 days will be used to assess whether mean log-eGFR are different between the two treatment arms, adjusting for adjusting for donor type (living vs deceased donor), participant weight pre transplant (<20kg vs ≥20kg pre-transplant) and transplant centre as a random effect.

Other electrolyte abnormalities within the first 72 hours post transplantation This includes the following:

- Hypernatraemia (defined as plasma sodium concentration > 145mmol/l)
- Hyperkalaemia (defined as plasma potassium concentration > 5.5mmol/L)
- Hypokalaemia (defined as plasma potassium concentration < 3.5mmol/L)
- Non anion-gap acidosis (defined as plasma bicarbonate < 20mmol/L and anion gap < 20mmol/L. Anion gap will be calculated as the sum of plasma sodium and plasma potassium, minus the sum of plasma chloride and plasma bicarbonate).
 Where possible, these components should be obtained simultaneously, but where this is not possible, samples should be collected within an hour.
- Hyperglycaemia (defined as random blood glucose > 5.5 mmol/L)

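### Day-1 eGFR comes from a steady-state formula while creatinine is still falling, and the pooled day 1/3/7 model does not adjust for pre-transplant creatinine

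*SAP*

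**What the plan says.** SAP section 3.4 (transplant kidney function) uses one formula at every time point, "eGFR = 36.5 x (height/ plasma creatinine concentration"), with no term for a changing creatinine. For days 1 and 3 the sampling rule is: "we will use the last measurement taken for each day, as this is likely to be the lowest and gives most time for creatinine to"; the stated aim is steady state.

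A single repeated-measures model is then used to "assess whether kidney function over days 1,3 and 7 are different between the two treatment arms". Its fixed covariates are given as "adjusting for donor type (living vs deceased donor), participant weight pre transplant (<20kg vs ≥20kg pre-transplant) and day of measurement", and it has random effects for participant and centre. Pre-transplant creatinine is not a covariate and there is no treatment-by-day term. The kidney function table in section 4.4 shows means and SDs for each day, but only one mean difference and one p-value for days 1, 3 and 7 together. Day 90 has its own model. The log-eGFR fallback lists donor type, weight group and the two random effects, and no longer lists day.

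Whether pre-transplant creatinine is available has to be inferred:
- The schedule in section 2.1 ticks "Blood Results" at the pre-transplant baseline and at transplant.
- Section 1.4 lists creatinine in the panel, but in a sentence about post-operative sampling.
- Section 3.7 uses a pre-transplant plasma sodium as a reference value.
- Creatinine is not in the baseline table of section 4.2.

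**The concern.** The formula equates creatinine with GFR only when production and clearance are in balance. After a transplant, creatinine starts at its pre-transplant level and falls towards the level set by the new graft. Until it arrives, the computed eGFR mixes three things: graft function, the starting creatinine, and the hours elapsed. The SAP's reason for taking the last sample concedes that creatinine is still moving. The choice shortens the remaining distance but does not remove it.

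At stake is a named secondary outcome with its own p-value. One of its three pooled time points partly reflects a baseline value that the model ignores. A reader of the results table would take the day-1 figure and the pooled difference as kidney function.

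**Working it through.** The SAP gives no SD, effect size or power for eGFR, so it has no figure of its own to reproduce. The check asks what its formula returns when true graft function is known.

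**Inputs from the SAP.** The formula, with height H in cm and creatinine in micromol/L; the sampling rule; the pooling of days 1, 3 and 7; and 128 evaluable patients (section 1.6), that is 64 per arm.

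**Assumptions, not in the SAP.** One compartment of 0.6 L/kg; constant GFR from time 0; starting creatinine C0 of 300, 600 or 900 micromol/L; samples at 24, 72 and 168 h; body surface area (BSA) from height and weight.

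**Formulas.**
- Css = 36.5 × H / GFR
- k = GFR × (BSA/1.73) / (0.6 × weight)
- C(t) = Css + (C0 − Css) × exp(−kt)
- reading = 36.5 × H / C(t)

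**Worked case: 130 cm, 30 kg, true GFR 60, C0 600, 24 h.** Css = 4745/60 = 79.1 and k = 0.12 per hour. C(24) = 79.1 + 520.9 × exp(−2.89) = 108.1, so the reading is 4745/108.1 = 43.9.

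**Readings for the 130 cm, 30 kg child, C0 = 300 / 600 / 900**

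| True GFR | 24 h | 72 h | 168 h |
|---|---|---|---|
| 60 | 51.9 / 43.9 / 38.0 | 60.0 / 59.9 / 59.9 | 60.0 throughout |
| 30 | 24.8 / 18.1 / 14.2 | 29.7 / 28.9 / 28.3 | 30.0 throughout |
| 10 | – / 8.6 / 6.4 | – / 9.4 / 8.3 | – / 9.9 / 9.7 |

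(At GFR 10, Css is 474.5, so a start of 300 would rise rather than fall and is left out.) At GFR 20 the 72 h reading runs from 19.7 to 17.3. Children of 95 cm/14 kg and 160 cm/50 kg show the same pattern.

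**Size on day 1.** Starting creatinine alone lowers the reading by (51.9 − 38.0)/51.9 = 27% at GFR 60 and by (24.8 − 14.2)/24.8 = 43% at GFR 30.

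**Sampling time.** Section 3.4 gives no clock time for the last day-1 sample. At 12 h, GFR 60 reads 36.2 / 23.5 / 17.4. At 48 h it reads 59.5 / 58.8 / 58.1, and GFR 30 reads 28.6 / 26.0 / 23.8. The fluid table in section 4.5 runs from the operation through days 1 to 3 to a 72-hour total, which fits a day 1 ending near 24 h but does not settle it.

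**Effect on the comparison between arms.**
- *Bias.* In simulation with randomisation and no true effect, the unadjusted day-1 comparison had mean difference 0.00 and type I error 5.0%.
- *Chance imbalance.* With an assumed coefficient of variation (CV) of 0.4 for starting creatinine, the SD of the between-arm difference in mean log C0 is √ln(1 + 0.4²) × √(2/64) = 0.385 × 0.177 = 0.068. A 1.96-SD imbalance is exp(1.96 × 0.068) = 1.14, or 14%. It moves day-1 eGFR by 4–9%, and day-3 eGFR by 0–1% at GFR 30–60 or 4% at GFR 10.
- *Precision.* The table shows the effect of adding log pre-transplant creatinine, scaled by height, with an assumed CV of graft GFR of 0.3 or 0.6.

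| Median GFR | Day-1 variance removed | Fall in standard error, day 1/3/7 average |
|---|---|---|
| 60 | 2–7% | 0.2–0.6% |
| 40 | 6–16% | 0.5–1.5% |
| 25 | 13–34% | 1.1–3.6% |
| 10 | 43–70% | 4.2–12.5% |

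On day 3 the variance removed is 0–1% at GFR 25–60 and 5–14% at GFR 10.

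**The case against.** The strongest reply is that the analysis is valid as written. Treatment is randomised, so pre-transplant creatinine is balanced in expectation, and the null simulation shows no bias. The SAP sees the steady-state issue and eases it with the last-sample rule. It tabulates each day's means by arm, gives day 90 its own model, and says that the study is powered only for the primary outcome. All of this stands.

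A reader might go further and infer that the whole day 1–7 comparison is uninterpretable, or that day 3 is as unreliable as day 1. The figures do not support this: with a working graft, day 3 is within a few per cent of the true value. Nor should the starting level be put down to dialysis, because section 4.2 has a category for pre-emptive recipients.

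Two tempting remedies would do harm. A creatinine reduction ratio depends more on the starting value. For a 15 kg, 95 cm child with GFR 60 at 72 h, Css is 36.5 × 95/60 = 57.8, so the reduction is 81%, 90% or 94% for starts of 300, 600 or 900, while eGFR reads 60.0 each time. Excluding children dialysed after transplant would condition on a post-randomisation event and remove the worst grafts.

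What the reply leaves standing is that the single reported difference includes a day-1 part that is not GFR, and that a probably available covariate would reduce its noise.

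**Conclusion.** The point holds in limited form. Day-1 eGFR is not at steady state and depends materially on pre-transplant creatinine: 52 to 38 for a true GFR of 60, and 25 to 14 for a true GFR of 30, at 24 h in a 30 kg child. Day 3 is materially affected only with poor function, and day 7 hardly at all. The between-arm test is not biased. The pooled difference carries avoidable noise and chance baseline imbalance, and its day-1 component should not be read as GFR.

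These sizes rest on the one-compartment model, on constant GFR from time 0, on starting values of 300–900 micromol/L and on a 24 h sample; a later sample shrinks the effect and an earlier one enlarges it. The gain in the pooled standard error is small unless graft function is poor. Only a secondary outcome is concerned; the primary analysis and the sample size are untouched.

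**What to change.** In section 3.4:

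1. Add log pre-transplant plasma creatinine, interacted with day, to the repeated-measures model. First confirm that it is in the blood-results extract, since the SAP implies this without saying so.
2. Add a treatment-by-day term and report the treatment difference with its interval for days 1, 3 and 7 separately. State which model supplies the pooled difference and its p-value.
3. Base the interpretation of kidney function on day 7 and day 90, and label the day-1 value as not at steady state.
4. Put day back into the log-eGFR fallback, where it matters most because creatinine changes over these days.
5. Keep eGFR as the outcome and keep all transplanted children in the analysis, including those dialysed afterwards.

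The cost is SAP wording, extra rows in the section 4.4 table and one covariate. Section 3.8 says that all adjustment factors will always be known. That would no longer be assured, so a line is needed on how a missing pre-transplant creatinine is handled.
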